3.4 Rationale for Study Design and Subject Selection

Currently there have been limited prospective studies using vulvoscopy with detailed photography demonstrating visible changes to the vulva, vestibule and vagina following oral administration of 60 mg ospemifene in post-menopausal women with VVA and dyspareunia. Information regarding visible changes to the vulva, vestibule and vagina may be very important to the patient and to the health care provider to best understand the beneficial effects of ospemifene and to ensure patient compliance with treatment.

This study is being conducted in an unblinded fashion because the primary endpoint is a collection of photographs. All subjects will receive the same active drug at the same dosage.

4. Selection and Withdrawal of Subjects

The study population will include menopausal females with vulvar vaginal atrophy (VVA) causing dyspareunia.

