9.6 Case Report Forms, Data Handling, and Recordkeeping

The following procedures will be employed related to recording of data:

- Relevant information determined at each Subject visit is to be recorded on source documents/CRFs.
- Data recorded on CRFs will be documented in an anonymous fashion with the Subject identified only by her Subject number and initials.
- All CRFs are to be completed in a neat, legible manner to ensure accurate communication of data. A black pen is preferred to ensure clarity of any reproduced copies. Any change or corrections made on the CRFs must be dated and initialed by the person making the change. In such cases, the best procedure is to cross out the original entry with a single line. Do not erase, overwrite, or obliterate, by any means, the original entry.
- CRFs and any data queries should accurately reflect Subject data records (source documents).
- The completed CRF set for each Subject is to be reviewed by the Principal Investigator for completeness and accuracy. The Principal Investigator will sign and date the last CRF page to indicate this review was performed.

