AN OPEN-LABEL PILOT PROSPECTIVE VULVOSCOPY WITH PHOTOGRAPHY  
STUDY OF THE VISIBLE CHANGES IN THE VULVA, VESTIBULE AND VAGINA PRE-  
AND POST- TWENTY WEEKS OF DAILY ADMINISTRATION OF 60 MG  
OSPEMIFENE IN POST-MENOPAUSAL WOMEN WITH DYSPAREUNIA FROM  
VULVAR VAGINAL ATROPHY

NCT 02784613  
April 4, 2016

Each subject's baseline and end of the study vulvoscopic photographs were subsequently assessed using a four-point rating scale, the vulvoscopic genital tissue appearance (VGTA) scale. The VGTA scale has not been validated. This scale assesses ten different parameters of the appearance of the genital tissue including loss of labia majora, loss of labia minora, decreased size of glans clitoridis, prominence of urethral meatus, stenosis of introitus, vestibular pallor, vestibular erythema, loss of vestibular moisture, loss of vaginal rugae, and loss of prominence of the anterior vaginal wall (Table 2). Each subject could score between 0 and 30 total points on the VGTA at each visit. A higher score of the VGTA scale was considered consistent with a worse vulvoscopic genital tissue appearance.

Baseline physical examination was performed as part of the screening. The physical exam included performance of a cotton-tipped swab testing where the examiner applied gentle pressure at each location of the vestibule: 1:00, 3:00, 5:00, 6:00, 7:00, 9:00, and 11:00 o'clock. The subject was asked to rate her pain on a scale from 0 to 3. Aggregate pain scores at baseline and study end were compared using the Wilcoxon signed-rank test.

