Baseline sexual function diary data concerning dryness and sexual pain were collected. The questions of the sexual function diary have not been validated. For 4 weeks prior to each study visit, subjects recorded yes or no answers to the following questions for each sexual encounter: 1) did the subject experience dryness before and were you now less dry, 2) did the subject use lubricant during this sexual activity, 3) did the subject experience pain/discomfort during foreplay? 4) did the subject experience pain during masturbation, 5) did the subject experience pain during oral sex, 6) did the subject experience pain during intercourse, and 7) did the subject stop early because of discomfort. Diaries were collected and new ones administered at each subsequent visit. The number of total sexual events, as well as percentage of total sexual events with pain or lubrication difficulty was compared for diaries collected at week 0 and week 20 using the Wilcoxon signed-rank test.

At the completion of the study, the photographs were sorted by subject number and date of exam and assessed by the principal investigator, a sexual medicine physician, who had not examined any of the women in person. He assigned scores to the photographs using pre-determined Likert scales for the 10 parameters of VGTA scale (Table 2). Differences in pre-and post-treatment scores were compared using Wilcoxon signed-rank test for non-parametric matched pairs. All tests of significance were 2-tailed with  $p < 0.05$  considered significant. All analyses were performed in Stata®, version 13.

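### The photographs are read in date order with no masking of visit described, so the tested VGTA change is open to reader bias

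*SAP*

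**What the plan says.** The only account of how the photographs were read is in the last paragraph of the unnumbered SAP: "the photographs were sorted by subject number and date of exam and assessed by the principal investigator". It adds that this reader had not seen the women in clinic, and that "He assigned scores to the photographs using pre-determined Likert scales for the 10 parameters of VGTA scale". Then "Differences in pre-and post-treatment scores were compared using Wilcoxon signed-rank test for non-parametric matched pairs", two-sided at 0.05.

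Earlier the SAP says that "baseline and end of the study vulvoscopic photographs were subsequently assessed using a four-point rating scale", that "Each subject could score between 0 and 30 total points on the VGTA at each visit" (higher is worse), and that "The VGTA scale has not been validated".

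The Protocol is silent on reading conditions:

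- Section 3.4: "This study is being conducted in an unblinded fashion because the primary endpoint is a collection of photographs".
- Section 7.2 deals with blinding of study medication only.
- Section 8.2 compares photographs across visits and tabulates the proportion improved. It names no reader, reading order or masking.
- Section 9.6: "The completed CRF set for each Subject is to be reviewed by the Principal Investigator for completeness and accuracy". CRFs carry the subject number, which is also a sort key for the photographs.

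**The concern.** Every woman takes the drug, so her earlier image is untreated and her later one treated. A reader who knows the date order knows treatment status. The natural reading of the SAP sentence, though it is not stated outright, is that the reader had that order in front of him.

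Open-label treatment does not force this. Section 3.4 explains why treatment is unblinded, but stored images can be coded and shuffled long after the visits. The two safeguards the SAP does name, no clinical contact with the women and pre-set scales, do not conceal which image came later.

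At stake is the only photographic outcome with a significance test, in a study whose primary endpoint is photographic. It is scored by one reader on an unvalidated scale with graded judgements such as pallor, erythema and moisture. A small, consistent tendency to score later images lower passes directly into the signed-rank statistic.

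**Working it through.** The plan gives no SD, effect size or power calculation, so it has no figure of its own to reproduce. What follows illustrates how little reader drift is needed.

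**Inputs from the documents:** 10 women (Protocol 8.1); paired signed-rank test, two-sided, 0.05 (SAP); ten parameters, total 0–30 (SAP). **Assumed:** no true change, the size of the reader shift, the SD of the paired difference, and the item noise rates. The SAP does not say whether the p-value is exact or approximate, so both are shown.

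**1. Threshold, no SD needed.** Suppose k women score one point lower at the later visit and the rest do not change.

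- Exact, zeros dropped: p = 2 × (1/2)^k. For k = 5, 2/32 = 0.063; for k = 6, 2/64 = 0.031.
- Normal approximation adjusted for ties and zeros, no continuity correction: z = k/√k = √k. For k = 4, z = 2.00 and p = 0.046 (exact 0.125).

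If one woman also moves one point the other way, there are m = k + 1 non-zero differences.

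- Exact: p = 2(1 + m)/2^m. For k = 7, 18/256 = 0.070; for k = 8, 20/512 = 0.039.
- Approximate: z = (k − 1)/√(k + 1). For k = 7, 6/√8 = 2.12 and p = 0.034.

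**2. Test on the 0–30 total.** Differences were drawn as rounded normal values with mean equal to minus the shift (10,000 runs). Proportion with p < 0.05, exact / approximate:

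| Assumed SD | no shift | 0.5 point | 1 point | 2 points |
|---|---|---|---|---|
| 2 | 0.033 / 0.048 | 0.077 / 0.101 | 0.226 / 0.272 | 0.743 / 0.777 |
| 3 | 0.040 / 0.046 | 0.057 / 0.069 | 0.133 / 0.149 | 0.414 / 0.437 |
| 4 | 0.040 / 0.045 | 0.054 / 0.057 | 0.096 / 0.100 | 0.260 / 0.272 |

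**3. Tests on the ten parameters separately.** Spread a 1- or 2-point total shift evenly: the reader lowers each item by one with probability 0.1 or 0.2. Noise of +1 and −1 each has probability q = 0.05, 0.1 or 0.2, and items are independent.

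- Exact rejection per item: 0.0007, 0.0024, 0.0093 (1 point); 0.0101, 0.0162, 0.0260 (2 points).
- Approximate rejection per item: 0.030, 0.048, 0.067 (1 point); 0.134, 0.134, 0.111 (2 points). At q = 0.2 the approximate rate is already about 0.048 with no shift, so only the excess is due to the reader.
- At least one of ten items significant, exact, from 1 − (1 − p)^10: 0.7–9% at 1 point, 10–23% at 2 points.

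These item assumptions imply a total-score variance of 10 × [2q + π(1 − π)], where π is the lowering probability. The SD therefore runs from √1.9 = 1.4 to √5.6 = 2.4, and the SD 2 row above is the nearest comparison. There the exact total-score test rejects in 23% and 74% of runs, against at most 9% and 23% for any of the ten exact item tests.

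**The case against.** **The text may only be incomplete.** Sorting could mean filing before a masked read, and the SAP does not say who sorted or what was visible at scoring. This stands as a limit on certainty, and is why the remedy asks for a statement of what the reader could see. But no masking step appears in either document, and following the plan as written supplies none.

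**It is an openly disclosed pilot.** The Protocol's objective is to document visible change, its photographic analysis is a tabulation, and the SAP itself admits that the scale is unvalidated. True, but the SAP goes on to test VGTA differences at 0.05, and the disclosure covers treatment, not image scoring.

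**Masking gains little in a single-arm study.** Change over time and regression to the mean remain mixed with any drug effect, and a re-read after an unmasked read is weakened by recall. Both points are right. They limit what a masked result would prove; they do not justify leaving in a bias that is cheap to remove. The re-read also leaves the other on-treatment sessions unmasked, though the VGTA test does not use them.

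**The illustration is built on assumptions.** Correct. The threshold cases need the remaining women to show exactly zero change, which is artificial for a 0–30 total. For a single parameter, 6 of 10 lowered is an average shift of 0.6 point, three to six times the item shift in step 3. The figures show sensitivity, not the likely bias.

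**The CRF review adds little.** If dates were visible, order was known anyway. Whether the review came before scoring is not stated, so the conclusion does not rest on it.

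**Conclusion.** The concern holds. As written, the plan has the images arranged by date and scored by one reader, with no masking of visit and no random order, and then tests the before/after difference. That leaves the VGTA result open to order-driven reader bias. It does not show that bias occurred.

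Size depends on what is tested. An average shift of 0.5 point on the total matters little. A shift of 1–2 points matters clearly for a total-score test: 10–23% and 26–74% exact rejection for assumed SDs of 2–4, against 3–4% with no shift. It matters much less for any one exact item test, and less for the ten exact item tests together than for the total at a similar SD. Shifts, SDs, noise rates and item independence are all assumed.

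This should be fixed. Confidence is moderate, because the SAP wording leaves some doubt about what the reader saw.

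**What to change.** **If scoring is still to come**, replace the sorting sentence with:

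> For each woman, the one pre-treatment session designated in advance as baseline (screening or Day 0) and the end-of-study session are stripped of subject number, date and visit, given a random code held by existing site staff other than the reader, shuffled into a single list of 20 sessions, and scored by the same reader. Scores are locked before decoding and re-pairing by subject.

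Baseline must be named because Protocol sections 5.2 and 5.4 each schedule pre-treatment photographs.

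**If scoring is done**, as the SAP's past tense suggests, first state whether the reader could see date or visit order. If not, say how that was ensured. If so, label the scores as unmasked to visit and add a coded, shuffled re-read of the same 20 sessions by the same reader as a sensitivity analysis, noting possible recall.

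**In either case**, state whether the total, the ten parameters or both are tested, and whether p-values are exact or approximate. The conclusions should say that masking removes only order-driven reader bias and does not separate drug effect from change over time or regression to the mean.

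**Cost:** SAP wording plus 10 × 2 = 20 sessions and 20 × 10 = 200 parameter scores. I would judge this a few hours for existing staff; the documents give no figure. No visit, procedure or reader is added. The other five scheduled sessions per woman (four on treatment, one pre-treatment) are not re-scored. One limit remains: the reader may recognise a woman's anatomy.

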2. TRIAL OBJECTIVE

The primary objective of this study is to prospectively document, using vulvoscopy with detailed photography, the visible changes to the vulva, vestibule and vaginal region in post-menopausal women with dyspareunia taking 60 mg daily ospemifene for twenty weeks at 6 timepoints: baseline, 4 weeks, 8 weeks, 12 weeks, 16 weeks and 20 weeks.

Secondary objectives include changes in pain as noted on the pain scale (appendix 2) and the q-tip test, in the vestibule on visual scale (appendix 3) by the clinician and sexual function by subject diary (appendix 4).

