8.1 Determination of Sample Size

The sample size of 10 menopausal Subjects was chosen for this study based on this being a pilot study and this sample size will be sufficient to prospectively document visible changes to the vulva, vestibule and vagina in post-menopausal women with VVA and dyspareunia. There will be a total of 6 photographic sessions of the vulva, vestibule and vagina over the 20 weeks of the study. The photograph(s) at baseline (vulvoscopy session 0) will be compared to photographs at 4 weeks (vulvoscopy session 1), 8 weeks (vulvoscopy session 2), 12 weeks (vulvoscopy session 3), 16 weeks (vulvoscopy session 4) and 20 weeks (vulvoscopy session 5).

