8.2 Photographic Data

Changes to the vulva, vestibule and vagina will be examined prospectively by comparing photographs of post-menopausal women with VVA and dyspareunia at 4 weeks, 8 weeks, 12 weeks, 16 weeks and 20 weeks while on treatment with 60 mg ospemifene. The proportion of subjects with improvement will be tabulated by scheduled visit.

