8.3 Patient Reported Outcomes

Mean pain score will be summarized at each scheduled visit. Subjects will also be categorized at each visit as having more pain, the same pain, or less pain compared to baseline.

Mean scores will be summarized for each item of the visual scale at each scheduled visit. Subjects will also be categorized at each visit as worsened, unchanged, or improved compared to baseline for each item of the visual scale at each scheduled visit.

For each subject, the proportion of total sexual events with a 'yes' response since the last scheduled visit will be calculated for each diary question at each scheduled visit.

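### The SAP applies unadjusted p<0.05 to roughly 4 to 20 tests and does not say which one tests the protocol's photographic primary endpoint

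*SAP*

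**What the plan says.** **Protocol.** Section 2 states the aim: "The primary objective of this study is to prospectively document, using vulvoscopy with detailed photography, the visible changes". Section 3.4 adds that "the primary endpoint is a collection of photographs". The analysis planned for them in Section 8.2 is a table: "The proportion of subjects with improvement will be tabulated by scheduled visit". Improvement is not defined there, no visit is singled out, and no test is given. The secondary outcomes in Section 2 are the pain scale, the q-tip test, the clinician's visual scale and the diary. Section 8.3 handles the visual scale descriptively: "Mean scores will be summarized for each item of the visual scale at each scheduled visit", with each woman also classed as worse, unchanged or better. Section 8 contains no hypothesis test and no significance level. Section 8.1 gives the basis for N: "The sample size of 10 menopausal Subjects was chosen for this study based on this being a pilot study".

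**SAP.** The photographs are scored on the VGTA, which does not appear in the protocol and which the SAP itself describes as not validated. "This scale assesses ten different parameters of the appearance of the genital tissue", and the total runs from 0 to 30. After the study the principal investigator scored the images: "He assigned scores to the photographs using pre-determined Likert scales for the 10 parameters of VGTA scale". Signed-rank tests are then applied to four kinds of outcome: VGTA scores, the aggregate swab pain score, the number of sexual events, and diary percentages. The closing rule is "All tests of significance were 2-tailed with" p<0.05 as the threshold. The SAP gives no primary test, order of testing or adjustment, and labels nothing exploratory. It mentions neither the visual scale nor, by name, the Appendix 2 pain scale.

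**The concern.** The protocol says what the primary endpoint is made of but not how it becomes a result. The SAP supplies a score and a test but does not say that this is the primary analysis. It gives every other comparison the same standing.

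The number of tests is also open. The VGTA comparison could be on the total, on the ten parameters, or on both. The diary percentages could be one composite figure or one for each of seven questions.

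With a single p<0.05 rule over all of these, any one of them can be reported as a significant change. A reader of the results could not tell the planned answer to the primary objective from the most favourable of several comparisons. The difference in outcome sets adds to this: a reader of both documents finds two clinician-rated scales that overlap on pallor, redness and dryness, and no statement of how they relate.

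**Working it through.** **Plan's own figures.** N = 10 has no effect size, standard deviation or power behind it, so there is no calculation to reproduce. The one checkable figure is the 0.05 level per test. For the signed-rank test with 10 non-zero, untied differences, 25 of the 2^10 = 1,024 sign patterns give a rank sum of 8 or less. The attainable two-sided size is therefore 2 × 25/1,024 = 0.0488, consistent with the stated level.

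**Counting the tests (SAP text).**
- VGTA: 1 (total), 10 (parameters) or 11 (both).
- Swab pain: 1.
- Number of sexual events: 1.
- Diary percentages: 1 (composite) up to 7 (one per question).

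**Chance of at least one p<0.05 if nothing changes, independent tests:** 1 − 0.95^k.

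| Reading | k | Result |
|---|---|---|
| VGTA total, swab, events, one percentage | 4 | 1 − 0.8145 = 18.5% |
| VGTA total, swab, events, seven percentages | 10 | 1 − 0.5987 = 40.1% |
| Ten parameters and total, swab, events, one percentage | 14 | 1 − 0.4877 = 51.2% |
| Ten parameters and total, swab, events, seven percentages | 20 | 1 − 0.3585 = 64.2% |
| No diary tests: VGTA total, swab | 2 | 1 − 0.9025 = 9.8% |
| No diary tests: ten parameters and total, swab | 12 | 1 − 0.5404 = 46.0% |

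Using the attainable size of 0.0488, k = 20 gives 63.3%.

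The rows without diary tests matter because the diary comparison may not be possible as written. The SAP compares diaries collected at week 0 with week 20. Protocol Sections 5.4 and 5.5 and Appendix 1 first dispense diaries on Day 0 and first collect them at Day 28.

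**Allowing for correlation.** Independence cannot hold throughout. Ten items scored 0–3 sum to 30, so the total is built from the parameters. The documents give no correlations, so 0 to 0.7 was assumed. The 20-test set was simulated under no change, with 10 women, 0–3 items for the VGTA and swab scores, continuous stand-ins for the diary outcomes, and signed-rank tests adjusted for ties and zeros. There were 2,000 runs per setting. The ranges cover within-woman correlations of 0.5 and 0.9.

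| Assumed correlation between outcomes | At least one p<0.05 |
|---|---|
| 0 | about 61–62% |
| 0.3 | about 54–55% |
| 0.5 | about 46–48% |
| 0.7 | about 35–39% |

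**Would adjustment be a better remedy?** Bonferroni thresholds are 0.05/4 = 0.0125, 0.05/14 = 0.0036 and 0.05/20 = 0.0025. The smallest exact two-sided p is 2/2^10 = 0.00195 with 10 non-zero differences and 2/2^9 = 0.0039 with 9. With 14 or 20 tests, only a result in which all ten women change in the same direction could pass. With nine non-zero differences nothing could. A single named primary test avoids this and keeps its own error at the nominal 5% (4.88% attainable).

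**The case against.** **This is a ten-woman, single-arm pilot.** Unadjusted p-values are defensible in that setting, and formal adjustment is close to unusable at this size. Both points stand, and they are why the remedy does not ask for adjustment. They do not excuse the absence of a label: the SAP declares results significant without calling any of them exploratory.

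**The primary outcome is identifiable.** A reader might infer that the trial has no primary outcome at all. The documents do not support that: Sections 2 and 3.4 name the photographs, and the VGTA is the only score the SAP takes from them. What is missing is the explicit link, the choice between total and parameters, and the deciding timepoint in the protocol.

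**The size depends on the reading.** A reader might infer that a false positive is more likely than not, or that about twenty tests are definitely planned. Neither follows. Twenty is the largest reading. The chance passes 50% only if the VGTA parameters are tested separately and the outcomes are weakly correlated.

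**The outcome mismatch adds no tests.** It is tempting to count the visual scale towards the error rate. Section 8.3 only summarises it, so its absence from the SAP leaves the figures unchanged. The overlap with the VGTA is also partial, since petechiae and friability are not VGTA parameters. The mismatch widens the choice of what to report, which these figures do not measure.

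**Conclusion.** The point holds. The SAP calls every signed-rank test significant at unadjusted two-sided p<0.05, names no primary test and labels none exploratory. The protocol's photographic endpoint has no score, deciding timepoint or test to settle the matter.

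On the test counts above, the chance of at least one false positive is about 19% to 64% under independence, or about 10% to 46% if the diary tests drop out. For the 20-test set it is about 35–48% at correlations of 0.5 to 0.7. Every one of these exceeds 5%. The spread comes from the ambiguous test count and from correlations that had to be assumed, so no single figure should be quoted as the trial's error rate.

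This should be corrected because it affects how results are read and the remedy is cheap. It does not show that any particular finding would be false.

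**What to change.** In the SAP:

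1. Name one primary test linked to the photographic endpoint. A reasonable choice is the change in VGTA total from baseline to week 20, by the signed-rank test at two-sided 0.05. State which pre-treatment session is the baseline, since Appendix 1 schedules vulvoscopy at both Visit 1 and Day 0.
2. Label the VGTA parameters, swab score and diary outcomes exploratory. Report them with estimates, 95% intervals and unadjusted p-values, and do not call them significant.
3. List which diary percentages are tested, and reconcile the week-0 comparison with the protocol's diary schedule.
4. Report the visual scale and pain scale descriptively, as Section 8.3 plans, and say how the visual scale relates to the VGTA.

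The primary test loses no power, and the other results are worded more cautiously. Bringing protocol Section 8.2 into line is more than an SAP edit: Section 9.1 requires a written amendment approved by the IRB. The SAP is written in the past tense, so if the photographs have already been scored, the report must disclose that the primary test was chosen afterwards. Naming it then would clarify the report but would not make the choice prospective.
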